Prior to launch of the study, all research personnel will receive training on human subjects' research, HIPAA, and biological safety, handling and transportation. The study designated graduate assistants will develop a study binder of all protocols and each role will be established so that appropriate blinding procedures can be maintained throughout the study duration. [name] and the study Project Manager will train all research personnel (graduate assistants and peer counselors) on the standardized intervention, scripts, protocols for women who need referrals or follow-ups for BF support or maternal well-being, documentation of schedule data collection visits and establish weekly research team meetings. [name] and the Project Manager will conduct internal audits every three months to ensure fidelity in recruitment and procedures.

Table 1: Timeline of procedures

Week	Day	Measure	Location	Time	Compensation
Prenatal visit	Recruitment	Study flyer, Breastfeeding Basic Information	HH, WAHS, UCHC prenatal clinic	5 min	\$0
0	Recruitment	Initial Screen	Hospital/ Smart phone	5 mins	
0	Baseline Assessment	Consent 
 
Verification of CLC evaluation of breastfeeding
 
Buccal cell swabs and/or blood collection (15 ml or 3 teaspoons)
 
QST
 
Questionnaires
 
Demographics
 
Breastfeeding Specific Factors: Maternal and Infant Breastfeeding History
 
	Hospital	1 hr Links will be shared for individuals to	\$25 UConn Greenphire Gift Card or ecard

		
 
• Breastfeeding Log (BL) 
 
◦ MAIBB-R
 
◦ Algorithm
 
 
 
• Breastfeeding Battery (BB) 
 
◦ BSES-SF
 
◦ Ongoing Breastfeeding Assessment
 
 
 
• Pain Interpretation Scales (PIS) 
 
◦ Coping Strategies Questionnaire
 
◦ McGill Pain Questionnaire
 
◦ Brief Pain Inventory
 
◦ Visual analogue scale
 
 
 
• Maternal Well-Being (MWB) 
 
◦ NINR CDEs (Anxiety, Sleep, Fatigue, Perceived Stress Scale, Index of Self-Regulation, Self-Efficacy for Managing Chronic Illnesses Scale, Global Health)
 
◦ EPDS
 
◦ Karitane Parenting Confidence Scale
 
 
 
		complete on their own	

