1	Days 1-5	Intervention Group ONLY: BL: 1 entry/ day Texts 2 times/ week breastfeeding coaching with links to Breastfeeding Modules 1-3 Maternal/Infant Care Modules 1-2	Personal computer/ smartphone	5 mins per entry  10 mins/ module	
	Days 1-5	Control Group ONLY: Texts 2 times/ week with links to Maternal/Infant Care Modules 1-2	Personal computer/ smartphone	10 mins/ module	
	Day 5	Both Groups: BB, PIS, MWB Control Group only: BL	Personal computer/ smartphone	10 mins	\$25 UConn Greenphire Gift Card or ecard
2	Days 8-12	Intervention Group ONLY: BL: 1 entry/ day Texts 2 times/ week breastfeeding coaching with links to Breastfeeding Modules 4-6 Maternal/Infant Care Modules 3-4	Personal computer/ smartphone	5 mins per entry  10mins/ module	
	Days 8-12	Control Group ONLY: Texts 2 times/ week with links to Maternal/Infant Care Modules 3-4	Personal computer/ smartphone	10 mins/ module	
	Day 12	Both Groups: BB, PIS, MWB Control Group only: BL	Personal computer/ smartphone	10 mins	\$25 UConn Greenphire Gift Card or ecard
3	Days 15-19	Intervention Group ONLY: BL: 1 entry/ day	Personal computer/	5 mins per entry	

		Texts 2 times/ week breastfeeding coaching with links to Breastfeeding Modules 7-9 Maternal/Infant Care Modules 5-6	smartphone	10mins/ module	
	Days 15-19	Control Group ONLY: Texts 2 times/ week with links to Maternal/Infant Care Modules 5-6	Personal computer/ smartphone	10 mins/ module	
	Day 19	Both Groups: BB, PIS, MWB Control Group only: BL	Personal computer/ smartphone	10 mins	\$25 UConn Greenphire Gift Card or ecard
Weeks 4-6	Days 21-40	Intervention Group ONLY: BL: 1 entry/ day Texts 2 times/ week breastfeeding coaching with links to Maternal/Infant Care Modules 7-12	Personal computer/ smartphone	5 mins per entry 5 mins/ module	
	Days 21-40	Control Group ONLY: Texts 2 times/ week with links to Maternal/Infant Care Modules 7-12	Personal computer/ smartphone	5 mins per entry	
Week 4	Day 26	Both Groups Infant development and play modules at 4 weeks	Personal computer/ smartphone	10 mins	

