Week 6	Day 40	Both Groups: 
 
• Buccal cell swabs and/or blood collection (15 ml or 3 teaspoons)
 
• QST
 
• BL
 
• BB, PIS, MWB
 
• Audio taped semi-structured interview: Reflection on participating in the study and the impact on their breastfeeding outcomes
 
	Clinic, smartphone	60 mins  15 mins	\$50 UConn Greenphire Gift Card or ecard
Week 8	Day 54	Both Groups Infant development and play modules at 8 weeks	Personal computer/ smartphone	10 mins	
Week 9	Day 61	Both Groups: BB, PIS, MWB, BL	Personal computer/ smartphone	10 mins	\$35 UConn Greenphire Gift Card or ecard
Week 12	Day 82	Both Groups: BB, PIS, MWB, BL Infant development and play modules at 12 weeks	Personal computer/ smartphone	10 mins	\$35 UConn Greenphire Gift Card or ecard
Week 16	Day 110	Both Groups Infant development and play modules at 16 weeks	Personal computer/ smartphone	10 mins	
Week 18	Day 122	Both Groups: BB, PIS, MWB, BL	Personal computer/ smartphone	10 mins	\$35 UConn Greenphire Gift Card or ecard
Week 20	Day 138	Both Groups Infant development and play modules	Personal computer/	10 mins	

		at 20 weeks	smartphone		
Week 24	Day 166	
Both Groups:
 
 
• Buccal cell swabs and/or blood (15 ml or 3 teaspoons) collection
 
• QST
 
• BL, BB, PIS, MWB
 
• Audio taped semi-structured interview: Reflection on participating in the study and the impact on their breastfeeding outcomes
 
• Infant development and play modules at 24 weeks
 
	
Clinic, Interview, smartphone
	
60 mins 15 mins
	\$75 + \$25 bonus UConn Greenphire Gift Card or ecard

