#### Self-Regulation Skills and Abilities.

**Index of Self-Regulation.** The Index of Self-Regulation is an NINR common data element used across several populations which assesses an individual's general behavior and change effort to make behavioral changes and modulate thoughts, emotions, and behaviors to achieve goals.

**Breastfeeding Algorithm.** An adaptation of the LATC scale, through texted UConn Health REDCap link women will assess daily (*BSM* intervention) or weekly (attention control) infant awake/sleep state, signs of hunger, number of attempts to latch, strength of latch and of suck, pattern of pauses and sucks, and time duration of BF sessions.

**Maternal Assessment of Infant BF Behaviors.** A clinical indicator of four infant BF behaviors based on the nursing personality assessment, maternal report, and digital recording of infant BF behaviors.

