**6) Potential risk for participant burden and inconvenience.** Based on our pilot study results, women reported the baseline data collection to be burdensome. We addressed this risk by removing several questionnaires to decrease participant burden and recruiting during the prenatal period. We anticipate by recruiting women during the prenatal period, women will be prepared for the time for participation and decrease the time burden. Women in the pilot study, reported that completing the paper BF diary 6 times a day was burdensome. For this project, we are using a text-based daily (one entry) BF diary. Women did not report the weekly measurements via UConn Health REDCap as burdensome and that the bi-weekly texting contact was supportive without burdening them to travel to face-to-face visits and places the mother-infant dyad at risk for illness, such as COVID-19. The initial data collection

appointment will take approximately 45-60 minutes. The daily breastfeeding log will take 5 minutes/1 times a day for the first three weeks and from 15 days to 6 weeks a weekly breastfeeding log for 5 minutes a day. The scheduled data collection at Weeks 1, 2, 3, 9, 12, and 18 will take 30 mins to complete. The scheduled data collection for Weeks 6 and 24 will take 60 minutes. Additionally, participants may find logging daily feeding behaviors and multiple questionnaires an inconvenience. Receiving regular texts about their breast-feeding status may also be inconvenient. However, there is evidence to show that support via email and text during the first few weeks of delivery can be beneficial to breast feeding behaviors.

**7) Potential risk for eye strain with prolonged period of time looking at the computer/text screen.** We will instruct participants to use a low light setting and the use of anti-glare software to reduce the strain. Participants will also receive reminders and daily surveys to complete, which may be inconvenient. The time commitment is explained in detail in the consent and will be verbally explained to each subject prior to signing the informed consent. Additionally, we will limit reminders to texts and text pushes via REDCap related to missing data and scheduling 6 week and 6-month research visits, with follow up phone calls as needed to encourage completion, or phone calls to address emergent clinical concerns to decrease the inconvenience to the participant.

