**8) Protection of risks related to BF and infant health outcomes.** Infants who BF or formula feed <6 times a day are at risk for dehydration and inadequate calorie intake. Women in the *BSM* intervention group will record daily number of feedings in their daily BF journal. Women in the attention control group will record the number of feedings per day once a week. A record of <6 feedings over a 24-hour period will trigger a notification email via UConn Health REDCap to the research team. The research nurse will contact the participant, evaluate the situation, and decide on the need for referral to a lactation specialist or their healthcare provider. This will also be done on a case-by-case basis. In our pilot study, no participants were referred for inadequate daily feedings. If the participant indicates they are having any difficulty such as mastitis or extreme pain, they will always be told to contact their PCP. Participants at every step of the research study will be encouraged to contact their provider if they are experiencing severe pain or discomfort such as fever.

**9) Protection of risks related to COVID-19 transmission.** Research team members will practice COVID-19 prevention measures at all points of face-to-face contact which include antenatal clinic, inpatient postpartum unit, follow-up data collection at 6 and 24 weeks at the Ambulatory Women's Health Services clinic, Hartford Hospital Lactation clinic, the School of Nursing BBL at UConn Health or UConn Health Outpatient Obstetrics/Gynecology Clinic. These measures will minimize personal density, allow distances, wear personal protective equipment and follow best practice consistent with CDC guidelines, state guidelines, and applicable University and hospital policies. In addition, the study design delivers standardized and best practice BF and BNP problem-solving skills during an acute period of pain when the rate of BF cessation is the highest via mobile technology and when face-to-face visits are most burdensome and places the mother-infant dyad at risk for illness, such as COVID-19.

**10) Protection of research team against biohazards.** All research teams will complete Biohazard and Transportation of Biohazard training through UConn Environmental Safety Department. Collection, or Hartford Hospital Health Stream, storage and assays of biohazardous samples will be performed in accordance with established safety guidelines and regulatory requirements.

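### The low-feeding alert relies on a weekly control-arm feeding record, but Table 1 schedules no control log between Day 19 and Day 40

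*Combined protocol and SAP*

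**What the plan says.** Item 8 of Protection against Risk treats fewer than six feedings a day as a hazard to the infant. BSM women record the number of feedings daily in their journal. For controls, "Women in the attention control group will record the number of feedings per day once a week". The safeguard acts on these records: "A record of <6 feedings over a 24-hour period will trigger a notification email", after which the research nurse contacts the woman and decides whether to refer her. Item 8 gives no end date for either arm's record.

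Table 1 (Design, Procedures, Materials and Methods) sets the schedule. After baseline, the control group has a breastfeeding log (BL) on Days 5, 12 and 19. For Days 21-40 the control row's measure cell holds only "Texts 2 times/ week with links to Maternal/Infant Care Modules 7-12". Day 26 adds "Infant development and play modules at 4 weeks" for both groups. The next control log is at the week 6 visit, Day 40. The BSM row for Days 21-40 lists one log entry a day. After week 6 both groups have the log at the same assessments, for example at Day 82: "BB, PIS, MWB, BL Infant development and play modules at 12 weeks".

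Two other places touch on the same weeks. The time cell of the control row for Days 21-40 allows five minutes for each entry, although the measure cell names nothing to enter. Item 6 of Protection against Risk, on participant burden, describes a daily log for three weeks and then, "from 15 days to 6 weeks a weekly breastfeeding log for 5 minutes a day", without naming an arm.

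**The concern.** A once-a-week record and a three-week interval cannot both be right. The alert can fire only if a count has been entered. A team that programs REDCap from Table 1 would leave control women without a scheduled count for most of weeks 4 to 6, while BSM women are prompted every day. What is at stake is a stated protection for infants in one arm, not an efficacy result.

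**Working it through.** No sample size or power figure is involved. The check compares the stated frequency with the days in Table 1.

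**Inputs.** Stated control frequency: once a week (Protection against Risk, item 8). Control log days after baseline: 5, 12, 19, 40, 61, 82, 122 and 166 (Table 1).

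**Intervals between control logs (later day minus earlier day).**

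| From | To | Gap in days |
|---|---|---|
| 5 | 12 | 12 - 5 = 7 |
| 12 | 19 | 19 - 12 = 7 |
| 19 | 40 | 40 - 19 = 21 |
| 40 | 61 | 61 - 40 = 21 |
| 61 | 82 | 82 - 61 = 21 |
| 82 | 122 | 122 - 82 = 40 |
| 122 | 166 | 166 - 122 = 44 |

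In weeks 1-3 the table matches item 8 exactly. The weekly pattern then stops.

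**Entries missing to week 6.** Continuing in steps of 7 from Day 19 gives 19 + 7 = 26, 26 + 7 = 33 and 33 + 7 = 40. Day 40 is listed; Days 26 and 33 are not. Four control logs are scheduled to Day 40 (Days 5, 12, 19, 40), against six if weekly.

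**Uncovered days.** Days 20 to 39 are 39 - 20 + 1 = 20 days with no scheduled control record. On Table 1's schedule, BSM women have 40 - 21 + 1 = 20 daily entries over Days 21-40; controls have one, on Day 40.

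**Could another instrument supply the count?** The breastfeeding battery, pain scales and well-being measures fall on Days 19 and 40 and on no day between. The Day 26 item is an educational module. Table 2 has no time point between 3 and 6 weeks, but it does not show the BSM daily entries either, so it does not settle the matter.

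**Could item 6 close the gap?** If its weekly log to 6 weeks means controls, Table 1 omits that log. If it means BSM, it conflicts with the daily BSM log on Days 21-40. Its two periods also overlap, since three weeks of daily entries run past Day 15. On neither reading does it agree with Table 1.

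**The case against.** The strongest reply is that this is a clerical slip. Elsewhere in Table 1 an entry means a log entry, and control rows in weeks 1-3 give their time per module. A time per entry in the Days 21-40 control row, together with item 6's weekly log to 6 weeks, points to a log line dropped from one cell. I think that is likely. It explains the gap without removing it, because the measure cell is what staff would program.

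A second reply is that the protocol uses weekly loosely. Data Collection during Follow up speaks of weekly pain at assessments that are not weekly, and item 5 has depression scores checked weekly although the scale is completed only at assessments. This has some force, but item 8 says once a week, and the first three control logs are exactly seven days apart.

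A third reply stands and shapes the fix. The link from the log to the feeding count is inferred. Table 1 defines the log as the infant-behavior assessment plus the algorithm, and neither is described as holding a 24-hour count. Item 8 names no instrument for controls.

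Three stronger readings are tempting and not supported:

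- A reader might take the Breastfeeding Algorithm paragraph, "or weekly (attention control) infant awake/sleep state, signs of hunger, number of attempts to latch", as a second source for a weekly feeding count. It lists infant state, latch, suck and session length, but no count. The count rests on item 8 alone.
- A reader might carry once a week through to Day 166 and call all the later gaps missing entries. Item 6 ends its weekly log at 6 weeks, Table 1 treats both arms alike after Day 40, and item 8's daily BSM sentence has no end date either. What is missing is an end date.
- A reader might treat daily BSM logging on Days 21-40 as settled and quantify the contrast between arms from it. Item 6 leaves that open.

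**Conclusion.** The inconsistency holds and is minor. As written, Table 1 leaves the low-feeding safeguard with no scheduled control record on Days 20-39: a 21-day interval where item 8 implies 7, and two entries short. The conclusion assumes that Table 1 is the schedule staff build from and that the control count is collected with the log. The documents do not show what REDCap actually sends, so they do not establish that control women went unmonitored.

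Other protections continue. Controls receive texts twice a week, all women are told to contact a provider if they have difficulty, and the pilot had no referral for inadequate feedings. No endpoint, analysis or power figure is affected.

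**What to change.** 1. In Table 1, Control Group row for Days 21-40, add one log entry on Day 26 and one on Day 33, five minutes each. Send the first with the 4-week infant module link already due on Day 26, and the second with one of the twice-weekly texts. Confirm that the control log holds the 24-hour feeding count and that the below-six alert is active for controls on both days.
2. In item 8 of Protection against Risk, state that the weekly control record runs to week 6 (Days 5, 12, 19, 26, 33 and 40), and that after week 6 both groups record feedings at the scheduled assessments (Days 61, 82, 122 and 166).
3. Ask the investigators which arm and schedule the log sentence in item 6 describes. Do not rewrite it until they answer, because the documents do not say whether it or the daily BSM row in Table 1 is right.

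**Cost.** Each control woman makes 2 x 5 = 10 minutes of extra entries, at most 2 x 140 = 280 entries across the arm, all on existing contacts. Daily journaling is a BSM component, so controls get slightly more exposure to logging: six entries to Day 40 instead of four. The longest control interval to week 6 falls from 21 days to 7, although the added entries fall on only 2 of the 20 uncovered days. If REDCap already sends these two prompts, only the text changes. Relaxing item 8 to match Table 1 would also make the documents agree, but it would keep the three-week gap.

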#### **Benefits:**

Based on our pilot results, we anticipate that participants in the *BSM* intervention group will have decreased BNP intensity and interference and an increase in BF exclusivity. Women may experience satisfaction that future women may benefit through our enhanced understanding of how self-management strategies may decrease BNP, increase BF exclusivity and identify genetic factors that place women at risk for BNP. However, it is possible that women will not perceive any benefit to study participation. Due to the physical, emotional and financial toll of BF pain and the minimal potential risks of the proposed study, the potential benefits to future patients far outweigh potential risks.

**Risk/Benefit Analysis:**

BNP is the leading reason 1 million women in the United States cease BF before 6 months, the optimal time for infant and women's health. Although there may be no direct benefit to participating in the study, there are minimal risks to participating. Thus, the risk/benefit analysis is dependent on the knowledge to be gained from the study overall. In light of the high likelihood of identifying characteristics (demographic, psychological and/or genetic) of BF pain that influence self-management process and outcomes, findings will be highly relevant to practice, easily accessible and clinically sustainable allowing for large-scale translation in health care and public health settings. In addition to the focus of the research, it is possible that unexpected and/or unrelated information will be discovered that is not the focus of this study. This information will not be disclosed to the participant or to their insurance company.

**Economic Considerations:**

There are no costs associated with study participation. Aligned with standard practices for increasing participant retention, we are using a scaled incentive plan. At enrollment, women will be informed they will be paid via a reloadable UConn Greenphire gift card or ecard (if they do not have a social security number) after each data collection point and if they participate at all data points, they will receive a study completion bonus. Participants will receive a \$25 at baseline, 1, 2, and 3 weeks, \$50 at 6 weeks, \$35 at 9, 12, and 18 weeks, and \$75 at 24 weeks, and \$25 as a completion bonus. They can potentially earn up to \$355 if they complete the entire study. This amount was derived from estimating the time dedicated to completing the study protocol at each time point.

**Data Management:**

Source documents (biological, sensory, and questionnaire data) are created for all subject contact protocols and must be initialed and reviewed by the Project Manager and the research team with oversight by the PI once a week. All data will be entered into a password-protected database stored on a firewall-protected server that is maintained by UConn. We will use the existing structure of data management established with our pilot study. The protocols established for trialing and monitoring UConn Health REDCap will be strictly followed. We have designed data collection forms to check for missing data in real-time to avoid incomplete data and routinely monitor data input. Our Project Manager will assist with downloading and updating the database, which will be reviewed during weekly team meetings. Audio files coded with subject ID, will be stored on UConn Onedrive. Only members of the research team has access to the files. Analysis and coding of the audio files will be conducted on UConn or HH laptops and computers.

**Data Safety Monitoring:**

We will have several mechanisms ongoing throughout the study as part of the Data Safety and Monitoring Plan and to monitor the potential occurrence of adverse events (AEs). First, the PI and the study staff (Drs. [name] and Project Manager) will oversee the day-to-day monitoring of all study activities. All data will be stored in locked cabinets within locked offices in the School of Nursing and password-protected computers. Electronic data will be encrypted for storage and de-identified for all study analyses. Data checks, for congruence and missing values, will occur weekly with double-checking (by two research study staff) to ensure accuracy.

Second, participants will be provided with day and after hours contact information for the PI and the study staff, and they will be instructed to report any, and all concerns related to study participation to the PI and/or the study staff. In addition, the PI will have weekly meetings with study staff to discuss study progress (recruitment, data collection and retention), any AEs that occur, and any issues that may arise during the study. Any adverse event that occurs will be directly reported by the PI to the IRB and

sponsoring agency within 24 hours of occurrence. Communication will occur through direct phone calls and follow-up email.

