### **Data Safety and Monitoring Board**

The PI will recruit three experts who are not involved with this research study to serve on an independent review committee. Members of the board will be experts in nutrition and BF, self-management related to pain, and genomic statistical methods. The Data Safety and Monitoring Board will review the study protocol prior to activation and develop a Data Safety and Monitoring Board plan. The Data Safety and Monitoring Board will evaluate the data on an ongoing basis and assure participant safety and study integrity. The Data Safety and Monitoring Board will be responsible for monitoring data and for making recommendations based on the data regarding appropriate protocol and any operational changes. The review committee will meet every 3 months to review progress, preliminary data, and any adverse events. They will meet with the PI and CoIs to make recommendations regarding the progress of the study and will be able to report to the Institutional Review Board of the University of Connecticut. Following review, the Data Safety and Monitoring Board will write a report outlining recommendations. These recommendations will be forwarded to the PI and the Institutional Review Board Chair at the University of Connecticut.

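### The 24-hour adverse-event report is timed from occurrence, but events at home are captured mainly if the woman volunteers them, so the deadline cannot be assured and capture is uneven between arms

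*Combined protocol and SAP*

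**What the plan says.** The rule is in the Data Safety Monitoring section: "Any adverse event that occurs will be directly reported by the PI to the IRB and" the sponsor, the sentence ending "sponsoring agency within 24 hours of occurrence". It has no limit by seriousness, relatedness or expectedness, and it does not mention awareness.

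The same section gives the general routes by which the team would hear of an event:

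- The PI and staff "will oversee the day-to-day monitoring of all study activities".
- Women hold daytime and out-of-hours telephone details for the team, and the reporting step is theirs: "they will be instructed to report any, and all concerns related to study participation to the PI and/or the study staff".
- Each week "the PI will have weekly meetings with study staff to discuss study progress (recruitment, data collection and retention), any AEs that occur".

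The Protection against Risk section adds specific routes. A record of fewer than six feedings in 24 hours "will trigger a notification email via UConn Health REDCap to the research team". Edinburgh depression scores are checked weekly, and a response that includes suicidal thoughts is notified at once. The same section tells women with mastitis, extreme pain or fever to contact their own provider.

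For the board, the Data Safety and Monitoring Board section states: "The review committee will meet every 3 months to review progress, preliminary data, and any adverse events".

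**The concern.** A deadline counted from occurrence can be met only if the team hears of the event within the same 24 hours. Most of follow-up is spent at home. The general route depends on the woman ringing or writing, and on her seeing the event as connected with the study. A woman admitted with a breast infection, or whose infant is taken to urgent care, has been told to go to her provider, and the protocol states no route from the provider back to the study team.

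Two things are at stake. Events learned of on the second day or later breach the reporting rule as written, however promptly staff then act, and events that are never volunteered may not be recorded at all. Second, the arms differ in how often women exchange information with staff, so a count of volunteered events partly reflects the amount of contact.

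**Working it through.** The plan states no figure to reproduce. The check sets the reporting rule beside the contact schedule.

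**Survey spacing.** Table 1 places the surveys at Days 5, 12, 19, 40, 61, 82, 122 and 166, with baseline taken as Day 0. Successive differences:

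- 5 − 0 = 5
- 12 − 5 = 7
- 19 − 12 = 7
- 40 − 19 = 21
- 61 − 40 = 21
- 82 − 61 = 21
- 122 − 82 = 40
- 166 − 122 = 44

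Surveys are therefore 5 to 7 days apart up to week 3 and 21 to 44 days apart afterwards. Every survey day except the week 18 one equals 7 × week − 2. On that pattern week 18 would be Day 124, and the last two gaps would be 124 − 82 = 42 and 166 − 124 = 42. The longest gap is thus 42 to 44 days, in weeks 18 to 24.

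**Missed surveys.** Under Post Enrollment Exclusion Criteria, a woman is removed only after three consecutive missed data points. One who misses Days 82 and 122 stays in the study with 166 − 61 = 105 days between completed surveys.

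**Other contacts after week 6.** Adding the infant-development modules (Days 54, 82, 110, 138, 166) gives contacts at Days 40, 54, 61, 82, 110, 122, 138 and 166. The gaps are 14, 7, 21, 28, 12, 16 and 28 days. The modules are educational and are not described as collecting events.

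**Content of the surveys.** None of the instruments in Tables 1 and 2 is described as an adverse-event question. The closest is the Ongoing BF Assessment Survey, described as covering breastfeeding experience, milk supply, problem-solving, therapies used and social support. That does not extend to medical events of mother or infant in general.

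**What each specific route covers.**

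- Feeding alert: one event type, resting on a daily record in the BSM arm and a once-weekly record in controls.
- Depression score: checked weekly. The immediate notice for suicidal thoughts depends on the woman's response.
- Staffed visits: baseline, week 6 and week 24 only.
- Day-to-day oversight: concerns study activities and is not described as asking women anything.

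**Arms side by side.** Up to week 6 both arms receive two texts a week. In the BSM arm these are coaching texts and come with a daily journal; in controls they are described as links to modules. Under Intervention Administration, the follow-up contacts at 1, 2, 3, 9, 12 and 18 weeks encourage completion and, for the BSM arm, also deal with breastfeeding concerns.

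**The case against.** The strongest reply is that the protocol has more routes than volunteered concerns and surveys. There is after-hours contact, the feeding alert, the depression and suicidality triggers, texting in both arms to week 6, and staff present at sensory testing and blood draws. Several of the listed study risks arise at those staffed visits. In weeks 1 to 3, which the protocol treats as the period of highest breast and nipple pain and cessation risk, surveys are at most 7 days apart. All of this stands. A reader might infer that events surface only through volunteered concerns, meetings and surveys, and that the reporting rule cannot be delivered at all. The documents do not support that: an event seen at a visit or phoned in promptly can be reported in time.

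A reader might also compute an average delay. With gaps g and events uniform over 166 days, Σg²/(2 × 166) = 4982/332 = 15.0 days, and 8/166 = 4.8% of events would fall within a day before a survey. The arithmetic is right, but it assumes that surveys are the sole route, that they reveal events and that risk is constant. The documents contradict the first, do not describe the second and do not support the third. These figures should not be read as real delays.

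A third inference would be that the board can act only after many more women have enrolled, for example 110/4 = 27.5 per quarter at the Year 2 and 3 rate. The documents do not establish this. The board is to evaluate data on an ongoing basis and to develop its own plan, which is not among them, and the IRB is already a 24-hour recipient. Notice to the board between meetings does not bear on whether the PI can meet the deadline; it is a separate matter for that plan.

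Finally, questionnaire items are not reproduced, so an event question could exist in an instrument described in other terms. That limits the finding to what is described. The protocol also plans no comparison of adverse events between arms, so the uneven capture matters only if counts by arm are produced.

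**Conclusion.** The concern holds in a limited form. As written, the rule cannot be assured for events at home that fall outside the specific triggers, and the weakness is greatest after week 6, when the twice-weekly texts end and surveys are 21 to 44 days apart (42 to 44 at most). Passive capture is richer in the BSM arm. No size can be put on the real delay or on the number of events missed, because the documents give neither event rates nor the speed at which women volunteer concerns. The conclusion rests on the instruments as described and on Table 1 as printed. It concerns safety reporting and leaves the efficacy analyses untouched.

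**What to change.** In the Data Safety Monitoring section:

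1. Start the 24-hour clock when any team member first learns of the event or REDCap first receives a report of it.
2. Add one short item, identical in both arms, to each existing REDCap survey, asking about new medical problems, urgent visits or admissions of mother or infant since the last survey. Link it to the REDCap email alert already used for fewer than six feedings.
3. Base any adverse-event counts given to the board on that item, so that they rest on the same question at the same times in both arms.

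The first change removes the conflict with the deadline. The second and third make capture more complete and more even, but leave the interval between surveys as it is.

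The cost is one item at each of the eight follow-up surveys, one alert and some protocol wording. Surveys become slightly longer, and staff will have more reports to handle.
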